6.3 Procedures for recording adverse events

All AEs will be recorded on the AE form . Only one AE will be reported on one form. For multiple AEs, multiple forms will be used. Study investigators will be responsible for codifying and keeping electronic copies of the form in the study database in protected files on the Pitt Research servers.

The Investigator-sponsor must be notified of the occurrence of any SAE within 24 hours of the investigator, designee, or site personnel's knowledge of the event. The Investigator-sponsor is responsible for notifying the appropriate health authorities (HAs), ethics committees (ECs), and investigators, of any expedited, annual, or other periodic safety reports in accordance with applicable regulations. Any safety report submission will cross reference the Amgen investigational new drug (IND) or clinical trial approval (CTA) number.

The Investigator is also responsible for notifying the local ECs in accordance with local regulations. Additionally, the Investigator-sponsor is responsible for reporting SAEs to Amgen.

SAE Reporting by Investigator-sponsor to Amgen

The Investigator-sponsor must inform Amgen in writing by e-mail or fax at the contact information listed below for all SUSARs that are judged as reasonably related to the Amgen study drug. Site will transmit the final CIOMS of that event to Amgen within twenty-four (24) hours of submitting the report to the applicable regulatory authority.

For regulatory reporting purposes, an event of "Death, Cause Unknown" from the study shall be processed as a SUSAR. All forms must be completed and provided to Amgen in English.

The Individual Case Safety Report (ICSR) may be referred to as an individual safety report or SAE Report, including Pregnancy Exposure Reports and Follow up Reports. The ICSR must be as complete as possible, at a minimum including event reference number, protocol name and number, investigator contact information, specific patient identifiers (e.g., initials, patient number, date of birth or age, or gender), the name of the suspect Study Drug, the date and dosage(s) of exposure, event, the date(s) of event, country of event, "Serious" Criteria, Relationship/causality of Study Drug, Hospitalization history for the event, Event status/outcome, Relevant history (including

diagnostics, laboratory values, radiographs, concomitant medications, and event treatment, and narrative summary.

Sponsor shall be responsible for collecting all SAEs and Pregnancy and Lactation Exposure Reports and will exercise commercially reasonable due diligence to obtain follow-up information on incomplete SAE or Pregnancy and Lactation Exposure Reports. In the event that the Company requires clarification or further information on individual SAE or Pregnancy and Lactation Exposure Reports, Company will not contact non-party investigators directly, but will route all such inquiries through Site for forwarding to such investigator(s). Site will be responsible to ensure such inquiries are completed and timely provided to Company.

Information not available at the time of the initial report (e.g., an end date for the SAE, discharge summaries, lot numbers, relevant laboratory values, scan data and autopsy reports) which are received after the initial report must be documented on a follow-up form, and submitted to Amgen in the same timelines as outlined above. Sponsor shall be responsible for obtaining follow-up information for the SAEs and demonstrate diligence in attempting to obtain such information by, among other things, maintaining written records of such attempts.

Other aggregate analysis including reports containing safety data generated during the course of the study is to be submitted to Amgen at the time the sponsor ISS submits to anybody governing research conduct i.e. RA, IRB etc. Final study report including unblinding data when applicable and reports of unauthorized use of a marketed product to be submitted to Amgen at the time the sponsor ISS submits to anybody governing research conduct i.e. RA, IRB etc. but not later than one calendar year of study completion.

Sponsor will provide an annual IND report to Amgen. Reports containing safety data generated during the course of the study is to be submitted to Amgen at the time the sponsor submits to anybody governing research conduct, i.e. regulatory authorities and IRBs. Sponsor will support reconciliation of all ICSRs at the end of the study at a minimum.

6.3.1 Diagnosis

If known, a diagnosis should be recorded on the AE form rather than individual signs and/or symptoms. However, if a constellation of signs and/or symptoms cannot be medically characterized as a single diagnosis or syndrome at the time of reporting, each individual event should be recorded as an AE or SAE. If a diagnosis is subsequently established, it should be reported as follow up information.

6.3.2 Persistent or recurrent AEs

A persistent AE is one that extends continuously, without resolution between patient evaluation time points. Such events will only be recorded once unless severity has increased since initial recording. If a persistent AE becomes more severe, it shall be recorded again.

A recurrent AE is one that occurs and resolved between patient evaluation time points and subsequently occurs again. All recurrent AEs shall be recorded again.

6.3.3 Abnormal laboratory values

Only clinically significant laboratory abnormalities that require active management will be recorded as AEs or SAEs. If the lab is a sign of a disease, only the diagnosis needs to be recorded. If the lab is not a sign of a disease, then the laboratory value or the designated term should be recorded (e.g., transaminitis or ALT 1750). Repeated observations of the same lab abnormality from patient contact time point to time point need not be recorded again unless they have worsened in severity (e.g., serum creatinine of 1.8 for 2 lab draws will only be recorded once).

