4.4.3 Safety outcomes

Safety outcomes of the study include the following:

- 4.4.3.1 Non-lung irreversible end-organ failure (e.g., end-stage renal disease) any time after day 1 attributable to carfilzomib.
- 4.4.3.2 Incidence of adverse effects (AE) requiring dose-modification (see section 5.3.1.2) any time during days 1-16.
- 4.4.3.3 Incidence of any AE at any time after day 1 as graded by the NIH Common Terminology Criteria for Adverse Events (CTCAE) (appendix B) criteria, as follows:
 - Grade 1: Mild; asymptomatic or mild symptoms; clinical or diagnostic observations only; intervention not indicated.
 - Grade 2: Moderate; minimal, local or noninvasive intervention indicated; limiting ageappropriate instrumental ADL (Instrumental ADL refer to preparing meals, shopping for groceries or clothes, using the telephone, managing money, etc.).
 - Grade 3: Severe or medically significant but not immediately life-threatening; hospitalization or prolongation of hospitalization indicated; disabling; limiting self-care ADL (self-care ADL refer to bathing, dressing and undressing, feeding self, using the toilet, taking medications, and not bedridden).
 - Grade 4: Life-threatening consequences; urgent intervention indicated.

Grade 5: Death related to AE.

- 4.4.3.4 Incidence of hypogammaglobulinemia any time after day 1.
- 4.4.3.5 Incidence of culture-proven *de novo* infection any time after day 1.
- 4.4.3.6 Diagnosis of systemic inflammatory response syndrome (SIRS) any time during days 1-16; requiring at least 2 of the following 4 criteria:

Body temperature: < 36 or > 38 degrees Celsius

Tachycardia: > 90 beats per minute

Tachypnea: > 20 breaths per minute

White blood cells: < 4000 or > 12000 cells/mm³

- 4.4.3.7 Patient death at any time after day 1 attributable to carfilzomib.
- A 1:1 retrospective control group including lung transplant recipients from the University of Pittsburgh with Antibody Mediated Rejection will be created to describe differences in the endpoints using the CFZ-based regimen vs. historic standard of care.

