5.13.2 Safety analyses

All AE data will be listed by patient, cycle, and dose. All AE occurring after informed consent is given will be summarized by event, system, and grade. All SAE will be listed and summarized separately.

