6.1.2 Adverse effect (AE) definition

An AE is any unfavorable and unintended sign, symptom, or disease temporarily associated with the use of an investigational medicinal product or other protocol-imposed intervention, regardless of attribution.

This includes the following:

AEs not previously observed in the patient that emerge during carfilzomib therapy (days 1through 16, and 28, 42, 90), including signs or symptoms associated with AMR that were not present prior to the AE reporting period.

Complications that occur as a result of protocol-mandated interventions.

AEs that occur prior to the assignment of study treatment that are related to a protocol-mandated intervention.

Preexisting conditions judged by the investigators to have worsened in severity or frequency or changed in character during carfilzomib therapy (days 1through 16, and 28, 42, 90).

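### Section 6.3.3 leaves unmanaged low-grade laboratory toxicity out of an adverse event outcome that is meant to count every CTCAE grade, and no planned laboratory summary recovers it

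*Combined protocol and SAP*

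**What the plan says.** Four parts of the combined protocol and SAP bear on which laboratory findings count as adverse events.

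- **Section 6.3.3 (abnormal laboratory values):** "Only clinically significant laboratory abnormalities that require active management will be recorded as AEs or SAEs". Active management is not defined. The section's own example of a repeated finding, "serum creatinine of 1.8 for 2 lab draws will only be recorded once", mentions no management.
- **Section 4.4.3.3 (safety outcome):** the incidence of adverse events of any CTCAE grade after day 1. Its Grade 1 text includes "clinical or diagnostic observations only; intervention not indicated".
- **Section 6.1.2 (definition):** "An AE is any unfavorable and unintended sign, symptom, or disease", with no condition that the finding be managed.
- **Section 5.13.2 (safety analyses):** "All AE occurring after informed consent is given will be summarized by event, system, and grade". Beyond this it provides AE listings and a separate SAE summary. It has no table of laboratory values, grades or shifts.

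Sections 4.4.3.3, 6.1.2 and 5.13.2 do not refer to 6.3.3. Section 4.4.3 also attaches a 1:1 retrospective control group to the safety outcomes, "to describe differences in the endpoints using the CFZ-based regimen vs. historic standard of care", without saying how adverse events or laboratory abnormalities will be ascertained in it.

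**The concern.** A reader of 4.4.3.3 and 5.13.2 would take the reported incidence to cover laboratory toxicity from Grade 1 upward. Under 6.3.3 it covers only the part that led to action. Whether a mild fall in platelets or rise in creatinine is counted then depends on what the investigator did about it, not on the value.

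This matters because cytopenias and creatinine rise are among the more frequent toxicities in the plan's own table in 6.1.4. The DSMB, which may stop the study only on safety grounds, reviews adverse event reporting (4.5) and so sees data that have passed through the same filter. The study also says in 3.1 that it will establish the safety of the regimen.

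**Working it through.** **Comparing the texts.** Take a laboratory value that is abnormal, unfavorable and left alone.

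1. Under 6.1.2 it can be an adverse event, since no management is required.
2. Under 4.4.3.3 it fits the Grade 1 description, since no intervention is indicated.
3. Under 6.3.3 it is not recorded, since it required no active management.
4. Under 5.13.2 it cannot appear, since that section summarizes recorded adverse events and plans nothing on laboratory values.

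The conflict is confined to laboratory findings. Symptomatic Grade 1 events are unaffected.

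**Do other planned outcomes recover it?** Only in part. Hypogammaglobulinemia (4.4.3.4, threshold in 4.3.9) is numeric and independent of 6.3.3. White cell count enters SIRS (4.4.3.6), over days 1-16 only. Events requiring dose modification are a separate outcome (4.4.3.2), and the table in 5.3.1.2 covers marked neutropenia, thrombocytopenia and nephrotoxicity. None of these reports milder cytopenia or milder creatinine rise by grade.

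**Possible size.** No figure in the plan rests on the rule, so there is none to reproduce apart from enrollment: 10 per year x 3 years = 30 (5.13.3), which matches the synopsis. The rates below come from 6.1.4.

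Patients whose event stayed below grade 3 = 30 x (any-grade % - grade 3 and above %) / 100.

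| Event | Any grade % | Grade 3+ % | Difference (points) | Of 30 patients | Share of any-grade events |
|---|---|---|---|---|---|
| Anemia | 45.9 | 22.5 | 23.4 | 7.0 | 51% |
| Thrombocytopenia | 34.9 | 23.2 | 11.7 | 3.5 | 34% |
| Neutropenia | 23.8 | 15.7 | 8.1 | 2.4 | 34% |
| Increased creatinine | 15.6 | 2.3 | 13.3 | 4.0 | 85% |

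The share is the difference divided by the any-grade rate, for example 13.3 / 15.6 = 85%.

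The patient counts are upper ends. They assume that no event below grade 3 is managed and that every event of grade 3 or above is recorded. If every event below grade 3 were managed, the loss would be 0. Section 6.1.4 does not split Grade 1 from Grade 2, so the range cannot be narrowed from the documents.

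**What is already captured.** Appendix B lists WBC, ANC, ALC, hematocrit, platelets and creatinine on each of days 1-16 and on days 28, 42 and 90. Hemoglobin, AST, ALT and bilirubin are among the tests drawn (5.4.1) but are not in the Appendix B list.

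**The case against.** The best defense is that 6.3.3 is simply the operational definition of a laboratory adverse event, and that 4.4.3.3 then grades whatever qualifies. The five-grade scale is generic, and limiting laboratory AEs to findings that matter is a defensible way to keep the forms usable. That is a fair reading of 6.3.3 and a good reason to keep it. It does not remove the problem, because 4.4.3.3 and 6.1.2 do not state the limit and the reported incidence would be read as covering all grades.

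The defense is also right that the consequences are bounded. The raw values are collected. Values severe enough to trigger 5.3.1.2 plausibly count as managed. Grade 2 is described in 4.4.3.3 as calling for minimal intervention, so many Grade 2 events would be recorded. The rates in 6.1.4 come from earlier carfilzomib trials, and most of the studies with available data described in 4.1 enrolled myeloma patients. Their transfer to lung recipients is an assumption.

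Three stronger readings are tempting, and the documents do not support them.

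- *Grade 1 laboratory events can never appear.* Active management is undefined, a mild abnormality that is treated would be recorded, and the creatinine example suggests that recording may not always need treatment.
- *Safety rests on AE forms alone.* The hypogammaglobulinemia, SIRS and dose-modification outcomes say otherwise.
- *The rule cannot be applied to the retrospective controls.* Nothing says so. Laboratory values and the treatments given for them are chart data, and 5.6 already takes standard-of-care results from medical records. The real gap is that no ascertainment rule for controls is written down. That gap affects all adverse events and is not caused by 6.3.3. The comparison is also descriptive only.

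**Conclusion.** The inconsistency is real and limited. Section 6.3.3 excludes laboratory findings that 4.4.3.3 and 6.1.2 would include, and 5.13.2 has no table that brings them back. The any-AE incidence will therefore understate low-grade laboratory toxicity by an amount that depends on investigator action.

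If the 6.1.4 rates held in 30 patients, the shortfall would be 0 to about 7 patients for anemia, 0 to 3.5 for thrombocytopenia, 0 to 2.4 for neutropenia and 0 to 4 for creatinine. These are ranges and should not be read as expected losses.

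For the control group, treated patients have daily laboratory tests on days 1-16 (Appendix A) and are questioned directly (6.2.2), while nothing is specified for controls. A described difference in laboratory toxicity could therefore partly reflect unequal ascertainment. The primary endpoint is not affected. This is a worthwhile, inexpensive improvement and not a defect that threatens the trial.

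**What to change.** 1. Keep 6.3.3 as the rule for the AE forms. Add to 4.4.3.3 a sentence saying that laboratory abnormalities enter this outcome only as recorded under 6.3.3, and cross-refer from 6.1.2.
2. Add to 5.13.2 a CTCAE grading by program of the values already captured: WBC, ANC, ALC, platelets and creatinine. Report worst post-dose grade and shift from day 1 for every patient who received carfilzomib, including any later replaced under 5.9. Give the number of patients with a value at each visit, because the later tests are standard of care and may be missing. Name the CTCAE version, since 4.4.3.3 gives only generic grade descriptions and no analyte cut-offs.
3. To cover anemia and liver toxicity as well, add the hemoglobin, AST, ALT and bilirubin results already drawn to the Appendix B data fields. Anemia has the largest figure in the illustration.
4. If laboratory toxicity is described against the retrospective controls, apply the same numeric grading to chart values in both groups, restricted to analytes and time windows available in both. State that sampling frequency may differ.

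Items 1 and 2 cost a sentence or two and a few programmed tables. Item 3 adds data entry. Item 4 needs chart abstraction whose extent depends on what the control records hold. No new tests are needed in treated patients. The visible consequence is that more low-grade events will be shown.

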6.3.4 Deaths

Deaths meet the criteria for SAE and all rules and regulations regarding reporting as defined in this section must be fulfilled. All deaths, irrespective of cause, will be recorded as SAEs and will be reported to the Sponsor. This includes death due to progression of AMR. Cause of death, if known, shall be recorded on the FDA Medwatch form. If deaths are due to progression of AMR, progression of study disease shall be recorded as a contributing factor. If deaths are due to study therapy, such notation shall be recorded as a contributing factor. If death occurs, it shall be noted on the FDA Medwatch form whether this death was expected or unexpected. After study completion (day 90), deaths due to progression of AMR shall only be recorded for the purposes of data analysis in the study.

6.3.5 Preexisting medical conditions

A preexisting medical condition is one that is present at the time of informed consent. Such conditions shall be recorded in the study database.

A preexisting condition will only be recorded as an AE or SAE if the frequency, severity, or character of the condition worsens during the study. When recording such events, the investigators will make note of the characteristics that have worsened (e.g., increased systolic blood pressure for preexisting hypertension).

6.3.6 Worsening antibody mediated rejection

Worsening or progression of AMR shall not be recorded as an AE or SAE. These data will be captured as efficacy assessment data only.

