4.5 Safety plan

Patients will be enrolled according to the inclusion and exclusion criteria established in section 5.3. Patients will provide informed consent to participate in this clinical trial. In the informed consent process, patients will be educated about the purpose for carfilzomib and the potential adverse effects as described in section 6.1.1. Adverse effects will be recorded and graded according to the CTCAE as described above in section 4.4.3. Serious adverse effects (SAE) will be reported timely as required and established in section 6.4.

A study data safety monitoring board (DSMB) will be established consisting of 3 members who represent non-funded non-investigators with no conflicts of interest regarding carfilzomib or the IST funding agency. The study investigators will invite qualified individuals to participate in the DSMB. The DSMB members will possess either PharmD, PhD, or MD qualifications and have a working knowledge of lung transplantation and AMR. The DSMB will be chaired by one of the three members as determined by the DSMB membership. The DSMB will meet once yearly to review study progress, to ensure appropriate enrollment milestones are being met, and to review the adverse event reporting. The DSMB will meet on an ad-hoc basis to review any SAEs.

The DSMB may terminate the study only after at least 15 patients have been enrolled. The DSMB may only terminate the study for safety reasons in which the perceived risks of continuing to provide carfilzomib to upcoming patients who may be enrolled outweighs the potential benefit to the patient and the allograft. The DSMB may not terminate the study for any reason related to carfilzomib efficacy.

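### Barring AMR worsening from AE/SAE recording conflicts with the plan's own AE definition and may leave non-fatal deterioration attributed to AMR out of the safety tables and DSMB review

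*Combined protocol and SAP*

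**What the plan says.** The rule in section 6.3.6 has two parts. The first is the exclusion: "Worsening or progression of AMR shall not be recorded as an AE or SAE". The second says where the information goes instead: "These data will be captured as efficacy assessment data only".

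Other sections deal with the same events differently:

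- **6.1.2** defines an AE "regardless of attribution". It covers events that emerge on therapy, "including signs or symptoms associated with AMR that were not present prior to the AE reporting period". It also covers "Preexisting conditions judged by the investigators to have worsened in severity or frequency or changed in character during carfilzomib therapy".
- **6.3.5** says: "A preexisting condition will only be recorded as an AE or SAE if the frequency, severity, or character of the condition worsens during the study". It makes no exception for AMR, and it defines a preexisting condition as one present at consent.
- **6.3.4** treats every death as an SAE and adds: "This includes death due to progression of AMR". After day 90, deaths from AMR progression are kept for analysis only.

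On oversight, section 4.5 has the DSMB review AE reporting once a year and adds: "The DSMB will meet on an ad-hoc basis to review any SAEs". The DSMB may stop the trial only for safety, not for reasons of efficacy. Section 5.13 places all aggregate analysis at study conclusion.

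**The concern.** Under section 5.1.1 a patient must already meet the AMR criteria to be eligible, so AMR is a preexisting condition in every participant. When AMR worsens, or a new AMR sign appears, 6.1.2 and 6.3.5 call for an AE record and 6.3.6 forbids one. Staff cannot comply with both, and no cross-reference says which prevails.

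This matters because of what AMR looks like. The allograft-dysfunction criteria in section 4.3.6 include a fall in FEV1, new hypoxemia needing oxygen, and mechanical ventilation. The carfilzomib table in section 6.1.4 lists respiratory reactions such as dyspnea, pulmonary edema and pulmonary embolism, and the same deterioration could come from either source. The trial is open-label and single-arm with only a retrospective control group, so the investigators choose the label knowing the treatment, and no concurrent group would show an excess. At stake is whether the safety outcome covering any AE (4.4.3.3), the AE and SAE summaries (5.13.2) and the reports reaching the DSMB are complete for the organ under treatment.

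**Working it through.** The plan states no figure on this point, so there is nothing to reproduce. The check is a comparison of the text, followed by a small calculation for scale.

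**1. Is AMR a preexisting condition under the plan's definition?** Section 6.3.5 requires presence at informed consent. Section 5.1.1 requires the AMR criteria to be met before a patient is approached for consent. The answer is yes for all patients.

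**2. What happens to a non-fatal event labelled worsening AMR?** Take a patient who newly needs oxygen after day 1.

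| Step | Section | Effect |
|---|---|---|
| Is it an AE by definition? | 6.1.2 | Yes, as a new AMR sign or a worsened preexisting condition, whatever the cause |
| How is it recorded? | 6.3.1 | A known diagnosis is recorded in place of the separate signs and symptoms |
| May that diagnosis be recorded? | 6.3.6 | No, neither as AE nor as SAE |
| Does a longer hospital stay bring it back? | 6.3.7 | No; the rule applies to an AE that prolongs the stay |
| Is severity and causality to carfilzomib assessed? | 6.2.3 | Only for AEs and SAEs that are recorded |
| Is it in the safety tables? | 5.13.2 | Only AEs and SAEs are summarized |
| Does the DSMB see it during the trial? | 4.5, 5.13 | No stated route; the DSMB reviews AE reporting and SAEs, and efficacy data wait for study end |

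Sections 6.3.1 and 6.3.6 act together: the first replaces the symptom with the diagnosis, and the second removes the diagnosis. If staff follow 6.1.2 or 6.3.5 instead, the same event is recorded. The result depends on which section the reader applies.

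**3. Do deaths close the gap?** For deaths to day 90, yes (6.3.4). The gap is confined to non-fatal events.

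**4. Scale, for context only.** The inputs are the rates in section 6.1.4 and the planned 30 patients. The assumption is that rates from earlier carfilzomib trials, which were not in lung transplant recipients, hold here. Expected number = 30 × rate; chance of at least one = 1 − (1 − rate)^30.

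- Dyspnea, grade 3 or higher, 4%: 30 × 0.04 = 1.2 patients; 1 − 0.96^30 = 0.71.
- Dyspnea, serious, 2.1%: 30 × 0.021 = 0.63 patients; 1 − 0.979^30 = 0.47.
- Pulmonary edema, grade 3 or higher, 1%: 30 × 0.01 = 0.3 patients; 1 − 0.99^30 = 0.26.

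These are counts of events that might need an attribution decision. They do not predict how many would be labelled AMR.

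**The case against.** The best defence is that 6.3.6 is a deliberate and specific rule. It treats progression of the study disease as an efficacy matter, and 6.3.4 is the carve-out that keeps deaths as SAEs. A specific rule can be read as qualifying the general ones in 6.1.2 and 6.3.5, which leaves only a missing cross-reference. Worsening is still captured, since 6.3.6 sends it to efficacy, and FEV1, biopsy findings and AMR-attributable death are secondary endpoints (4.4.2). Section 4.3.6 also requires that no other identifiable cause be present apart from cellular rejection, so a recognised drug toxicity should not be called AMR.

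Much of this stands. The death rule can be reconciled with 6.3.6, and the conflict that remains is with 6.1.2 and 6.3.5. The other points help less:

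- The condition in 4.3.6 belongs to the diagnosis of AMR; 6.3.6 does not cite it. It guards only against toxicity that someone has recognised. No section in the text reviewed defines worsening AMR or requires adjudication before the label is applied.
- Efficacy capture carries no AE grade or causality assessment and is analysed only at the end. Section 5.6 takes PFTs and biopsies from standard care and does not perform them solely for research, so capture may be incomplete.

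A reader might infer that drug-related respiratory harm labelled AMR could never reach the safety tables or the DSMB. The documents do not support that: deaths to day 90 are SAEs, non-fatal events are recorded wherever 6.1.2 or 6.3.5 is followed, and the data survive as efficacy data. A reader might also take the 27.6% any-grade dyspnea rate and conclude that about 8 of 30 patients (30 × 0.276 = 8.3) could be filed either way. That does not follow, because dyspnea is not itself a dysfunction criterion in 4.3.6, and nothing suggests that every case would be ambiguous.

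**Conclusion.** The conflict is real. Section 6.3.6 cannot be applied together with 6.1.2 and 6.3.5 as written, and the plan does not say which governs. Where 6.3.6 is followed, non-fatal respiratory deterioration attributed to AMR may be missing from the safety tables and from DSMB review, without a grade or a causality assessment.

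The size cannot be fixed from the documents. Under the transferred rates, severe or serious dyspnea would be expected in about one patient of 30 or fewer, so few events are involved. In a 30-patient trial whose DSMB may stop only for safety, however, one unreported serious respiratory event can matter. The conclusion rests on two conditions: that some toxicity may go unrecognised or be misattributed, and that at least some staff apply 6.3.6 over the general rules. This should be corrected. It does not show that the safety data will be wrong.

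**What to change.** - Reconcile 6.3.6 with 6.1.2 and 6.3.5, and state which rule governs AMR signs and worsening. Add a cross-reference to 6.3.4 for deaths.
- Record any new or worsening respiratory event that meets AE or SAE criteria, with CTCAE grade, causality to carfilzomib, and a yes/no field for attribution to AMR.
- In 5.13.2, tabulate safety twice: with and without the events attributed to AMR.
- In 4.5, state that AMR-attributed SAEs are part of DSMB review.
- Keep changes in FEV1, DSA and biopsy findings as efficacy data. The clinical event that meets AE or SAE criteria is what enters the safety record.

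The cost is a few more forms per patient, some additional SAEs for the DSMB to read, and a safety table that looks somewhat less favourable because it will include disease progression. The second tabulation lets readers separate the two. No treatment, visit or sample changes.
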